5.5 Key inclusion criteria

Patients must meet the following criteria to be eligible for the study:

1) Have a primary care physician at the University of Pennsylvania Health System; 2) Meets American College of Cardiology / American Heart Association (ACC/AHA) guidelines for statin prescription as follows: a) Any form of atherosclerotic cardiovascular disease (ASCVD); b) LDL-C levels of 190 mg/dL or greater on their most recent lipid panel; c) Age 40 to 75 years with diabetes and LDL-C levels of 70-189 mg/dL on their most recent lipid panel; d) Age 40 to 75 years with 10-year ASCVD risk of 7.5% or greater.

5.6 Key exclusion criteria

Patients will be excluded if any of the following criteria is met: 1) Allergy to statins; 2) Severe renal insufficiency defined as glomerular filtration rate (GFR) less than 30 mL/min; 3) Adverse reaction to statins including a) myopathy, ICD-10 G72.0 G72.9, ICD-9 3594 3599; b) Rhabdomyolysis, ICD-10 M62.82, ICD-9 72888; c) hepatitis, ICD-10 K716, ICD-9 5733

Physicians (and their respective patients) will be excluded if they have less than 10 patients among their entire panel that are eligible for a statin medication.

6. Subject recruitment

Information on primary care physicians and their patients at the University of Pennsylvania Health system will be obtained from the electronic health record using Penn Data Store and Clarity, an EPIC reporting database.

7. Subject compensation

No compensation will be offered in this study.

8. Study procedures

8.1 Consent

A waiver of informed consent is requested. This is a health system initiative that will be implemented. The study is to evaluate that initiative. Therefore, physicians and their patients will not be consented as this is the standard of practice per the health system initiative. Without a waiver of the consent, the initiative would still be implemented by the health system, but the study would be infeasible. There are several additional reasons why we feel a waiver of consent should be granted. First, it is not feasible to consent every patient and physician and as mentioned this initiative would occur with or without the study of it. Second, if members of the control group were consented, they would know they were being studied and this could change their behavior. This could potentially disrupt the design of the study and making interpretation of the findings challenging. Third, physicians are not being forced to prescribe statins for their patients. Instead, they are being reminded of evidence-based guidelines and offered an opportunity to review pertinent information and prescribe a statin. This is no different than standard of care in which a physician would review the same information and decide to prescribe a statin or not. The initiative is simply a reminder for the physician and makes their standard of care process easier to conduct.

8.2 Procedures

Data on primary care physicians and their patients at the University of Pennsylvania Health System will be obtained from Penn Data Store and Clarity (Epic's data reporting database). Physician data includes demographic information (age, race, gender, type of medical degree, etc.) and may be also obtained from publicly available databases or websites online. Patient information includes demographic information, information about comorbid conditions (including diabetes, hypertension, and chronic kidney disease, and comorbid conditions needed to calculate the Charlson Comorbidity Index, laboratory test results (total cholesterol, triglycerides, LDL-C, HDL-C, liver function tests, creatinine, and glomerular filtration rate), and any contraindications to statin prescription (allergies or history of adverse reactions).

After identifying eligible physicians and patients, block randomization will occur at the physician level using block sizes of three and stratifying by quartile of baseline statin prescribing rate.

9. Analysis plan

In the main analysis, we will perform unadjusted comparisons of the change in the percent of eligible patients that are prescribed a statin before and after the intervention by study group using chi-square tests. To evaluate the robustness of the findings, a multivariate logistic regression

model will be fit adjusting for baseline statin prescription status as well as patient and physician factors. Binary variables will be created for time (pre- and post-intervention), study arm (control or intervention), and statin prescription (no or yes). The outcome of interest will be the interaction between the binary variables time, study arm, and statin prescription. All hypothesis tests will be two-sided using an alpha of 0.017 as our threshold for statistical significance. Clustering will be conducted at the level of the physician.

10. Investigators

[name], MBA, MS is the Principal Investigator (PI) and is an Assistant Professor of Medicine and Health Care Management at the Perelman School of Medicine and The Wharton School at the University of Pennsylvania. He has past experience leading clinical trials to deploy interventions impacting patient care and outcomes. He currently spends 80% of his effort on research and 20% on clinical and teaching activities.

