5.1 Design

This study will use a randomized, controlled trial to evaluate a health system initiative. The electronic health record will be used to generate lists of patients who meet criteria for statin prescription using the 2013 ACC/AHA (American College of Cardiology / American Heart Association) guidelines. Primary care physicians at the University of Pennsylvania Health System will be randomly assigned to a control group with no intervention or one of two intervention groups as follows:

--Intervention 1: Active choice--

Primary care physicians will be prompted by email to review an online form with a list of their patients who are eligible for statin therapy but have not been prescribed one. Clinical information including the following will be presented for each patient (as available): age, history of atherosclerotic cardiovascular disease (ASCVD) or diabetes, recent test results including lipid profiles and liver function tests. If appropriate information is available, the ASCVD risk score will be calculated and displayed.

Using the form, the physician will be able to select atorvastatin 20mg for all of the patients or can individually review information for each patient and select from the following options: 1) prescribe atorvastatin 20mg once daily; 2) prescribe atorvastatin at a different dose (10mg, 40mg or 80mg); 3) prescribe a different statin (choose from simvastatin, pravastatin, or rosuvastatin); 4) do not prescribe a statin and select a reason (patient declined; patient allergy; other).

The online form will be created using a HIPAA compliant website on secure University of Pennsylvania Health System servers. The website will require the physician to sign in using their PennKey and password. Once the form is submitted, a member of the study team will enter the orders in EPIC for the physician to review and sign. The physician will receive notification that these orders have been entered and are ready to review. A letter to the patient will be generated describing the physician's review of their information, prescription of a statin, and the risks and benefits of taking a statin medication.

--Intervention 2: Active choice and social comparisons—

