5.4 Accrual

Primary care physicians at the University of Pennsylvania Health System will be randomly assigned to one of the three arms. Based on an initial data review, we have made the following assumptions: baseline statin initiation rate is about 65%, median number of patients eligible but not on a statin per primary care physician is 38, intracluster correlation for statin prescribing is 0.026. Given these baseline, we estimate that a sample size of 84 primary care physicians (28 per arm) will provide at least 90% power to detect a 10% difference between each intervention arm and the control arm, using a Bonferroni correction to define an alpha of .017 (three comparisons) as our threshold for statistical significance.

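### Physicians are randomised within quartiles of baseline prescribing rate but no analysis names the quartile; a physician-clustered test that omits it is unbiased but conservative, and adding it is an optional, cost-free gain

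*Combined protocol and SAP*

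**What the plan says.** Section 8.2 sets the allocation: "After identifying eligible physicians and patients, block randomization will occur at the physician level using block sizes of three", "stratifying by quartile of baseline statin prescribing rate". Each physician's quartile is therefore known before allocation.

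Section 9 gives two analyses. The first is "In the main analysis, we will perform unadjusted comparisons of the change" by study group, with chi-square tests. The second is a logistic model offered as a robustness check, "adjusting for baseline statin prescription status as well as patient and physician factors". The baseline status there belongs to the patient, and the physician factors are not listed, so the quartile may or may not be among them. Section 9 ends its statistical text with "Clustering will be conducted at the level of the physician". It does not say by what method, or whether this covers the chi-square.

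Section 5.4 plans for "a 10% difference between each intervention arm and the control arm, using a Bonferroni correction to define an alpha of .017 (three comparisons"). It does not mention the stratification. Dividing alpha by three implies a comparison between the two intervention arms, but no effect size is given for it.

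**The concern.** Stratified allocation balances the arms on whatever the quartile predicts. That variation drops out of the true sampling error of the arm difference. An analysis without the quartile still counts it as noise, so it reports a standard error larger than the design delivers. The test then rejects a true null less often than 1.7%, and its interval is wider than necessary.

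The link between quartile and outcome is close to mechanical in the intervention arms. If an intervention works by starting statins in untreated patients, a physician's change depends on how many untreated patients there were, and that is what the baseline rate measures. The stake is therefore greatest for the comparison of active choice with and without social comparisons. That comparison bears on the objective in Section 2 and has no planned effect size.

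**Working it through.** **1. The plan's own power figure.** Inputs from Section 5.4: 38 patients per physician ("median number of patients eligible but not on a statin per primary care physician is 38"), ICC 0.026, 28 physicians per arm, 65% against 75%, two-sided alpha 0.017.

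- Design effect = 1 + (38 − 1) × 0.026 = 1.962.
- Effective patients per arm = 28 × 38 / 1.962 = 542.3.
- Power = 88.8% (87.1% with a t-test on 54 degrees of freedom), close to the stated 90%.

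No stratification term enters this figure.

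**2. Follow-up rate only, 38 patients per physician.** The correlation (rho) between a physician's baseline and follow-up rates is not in the documents, so it is varied.

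| rho | Null rejection, without / with quartile | Power 65% vs 75%, without / with |
|---|---|---|
| 0 | 1.9% / 1.9% | 85.7% / 85.4% |
| 0.5 | 1.5% / 1.7% | not run |
| 0.8 | 1.0% / 1.7% | 86.7% / 90.9% |
| 1 | 0.7% / 1.6% | 88.2% / 93.6% |

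**3. Change in the same patients.** This is the closer reading. Section 8.2 identifies eligible patients before randomisation, and Section 5.1 shows each physician "a list of their patients who are eligible for statin therapy but have not been prescribed one".

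Assumed, not in the documents:
- panel of 38 / 0.35 = 109 patients (taking 65% as the share already on a statin), or 38;
- 3, 5 or 15% of untreated control patients start;
- 0 or 5% of treated patients stop;
- start rates with ICC 0.026, unrelated to the baseline rate;
- an effect of d points on the panel percentage adds d/0.35 to the start rate.

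There are 84 physicians in four strata of 21, with seven blocks of three in each. A linear model for the physician-level change is fitted on the 56 physicians compared: 54 degrees of freedom with arm alone, 51 with quartile terms. Each of 12 scenarios has 10,000 trials.

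| Contrast | SE excess without quartile | Null rejection without / with (nominal 1.7%) |
|---|---|---|
| Intervention vs control, null | 0 to 11% | 0.8–1.6% / 1.4–1.8% |
| Intervention vs intervention, both 10 points above control | 16 to 33% (up to 35% in a repeat run of some scenarios) | 0.1–0.6% / 1.5–2.0% |

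- Example, intervention vs control (panel 109, 15% start, 5% stop): true SE 0.0091; estimated 0.0101 without the quartile and 0.0091 with it. 0.0101 / 0.0091 = 1.11.
- A 10-point difference from control: power 99.9 to 100% either way; the interval is 7 to 17% narrower with the quartile.
- An assumed 2 to 3 points from control: power gain 0 to 13 points (for example 59% to 72%, or 88% to 91%).
- Between intervention arms: interval 14 to 25% narrower (1 − 1/1.16 = 14%; 1 − 1/1.33 = 25%). For an assumed further 3 points, power is 8 to 40% without and 24 to 63% with the quartile.

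**4. Sensitivity.**
- Start rates correlated −0.5 to 0.9 with baseline rate (panel 109): SE excess against control 0 to 24%; 10-point power still about 100%.
- Outcome restricted to untreated patients, 5% vs 15%: null SE 0.0135 and power 99.8% with or without the quartile. Between intervention arms the true SE is 0.0228, and the estimate is 0.0232 either way.
- Independent samples before and after (not what the text suggests): SE excess 4 to 33%, and a 10-point power loss of 1 to 29 points, depending on assumed panel size and correlation.

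**5. If clustering is ignored.** For a follow-up comparison with 38 patients per physician, the critical value 2.387 becomes 2.387 / √1.962 = 1.704. The nominal 1.7% becomes 8.8% (ignoring stratification).

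**6. Choice of standard error with quartile terms, 56 physicians, true null.**
- Model-based: 1.5 to 2.0% rejection.
- HC3 with t degrees of freedom: 1.0 to 1.4%.
- Uncorrected sandwich: about 2.5 to 3.0%.
- A three-arm linear model with one pooled variance, for the comparison between intervention arms: 2.2 to 4.0%, because the less variable control arm is pooled in.

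**The case against.** The strongest reply is that the plan's main test is a chi-square, and the conservatism belongs to a physician-level test that the plan does not spell out. This stands as a limit on the point. A reader might infer that the main analysis as written errs safely on the conservative side. The documents do not support that, because the clustering sentence may not cover the chi-square. If it does not, a follow-up comparison is anti-conservative (step 5).

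Second, the planned comparison loses nothing that matters: power for 10 points against control is about 100% either way in step 3. This also stands, and it is why the point is optional.

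Third, the comparison with most to gain is only implied by the three-way split of alpha. The further 3 points is an assumption, and power for it stays low even with the quartile. Section 9 codes arm as control or intervention and never says how the two intervention arms would be compared. All of that is fair, but it does not remove the precision gain.

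Fourth, if the outcome means new prescriptions among untreated patients, the gain vanishes when start rates are unrelated to the baseline rate. Correct. However, Sections 3.1 and 9 define a before-to-after change in the percentage of eligible patients, which favours the wider population.

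Finally, the unnamed physician factors might include the quartile. That could help only the robustness model, since the main analysis is expressly unadjusted.

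**Conclusion.** The point holds as one of efficiency. The allocation is stratified, the main analysis is unadjusted, and no analysis names the quartile. Given a test that accounts for physician clustering, the estimate is unbiased and the standard error is too large. The excess is about 0 to 11% against control under the null, and about 16 to 35% between intervention arms that both raise prescribing. The direction follows from the design. The sizes rest on the assumed panel sizes and start and stop rates, on following the same patients, and on how well the quartile predicts the change, for which the documents give no figure.

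Two further readings go too far. The omission does not bias or invalidate the trial. Nor can the adjustment be said to secure the stated 90% power: it lifts power past 90% in step 2 only if baseline strongly predicts follow-up, and in step 3 power was never short. The unclear clustering of the chi-square is a separate and larger matter.

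**What to change.** An optional improvement:

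- Make the primary analysis a physician-clustered comparison of the change that includes the randomisation quartile or the physician's continuous baseline prescribing rate.
- Fit each pairwise comparison on its own two arms, not in a three-arm model with one pooled variance.
- Use model-based standard errors with t degrees of freedom. If GEE or robust standard errors are preferred, specify a small-sample correction; with 56 physicians the uncorrected sandwich is too liberal.
- State whether physicians are weighted by panel size. Section 3.1 defines a percentage of eligible patients, whereas an unweighted physician-level model averages over physicians.
- State whether the clustering sentence covers the primary test, and list the physician factors.
- Report the unadjusted comparison as supportive.

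The cost is analysis-plan wording only: no new data and no change to sample size or allocation, since the quartile is already computed for every physician before randomisation.

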11.1 Data confidentiality

Computer-based files will only be made available to personnel involved in the study through the use of access privileges and passwords. Wherever feasible, identifiers will be removed from study-related information. Precautions are already in place to ensure the data are secure by using passwords and HIPAA-compliant encryption.

11.2 Subject confidentiality

Data on physicians and patients will be obtained from Epic and Penn Data Store. Any information that is obtained will be used for research purposes only. Information on patients will only be disclosed within the study team and to the patient's primary care physician. All study staff will be reminded of the confidential nature of the data collected and contained in these databases.

The Leonard Davis Institute's Health Services Research Data Center (LDI HSRDC) will be the hub for the hardware and database infrastructure that will support the statistical analysis. The LDI HSRDC is a secure computing environment for a large volume of highly sensitive data. All members that access data must complete HIPAA training including secure data transfer,

passwords, computer security habits and knowledge of what constitutes misuse or inappropriate use of the server. Only trained study staff will have access to the code that links the unique identifier to the subject's identity. Electronic data will be stored on secure, password-protected firewalled servers at the University of Pennsylvania.

11.3 Subject privacy

All efforts will be made by study staff to ensure subject privacy. Data will be evaluated in a de-identified manner whenever possible.

11.4 Data disclosure

Information on patients will only be disclosed within the study team and to the patient's primary care physician (to whom this information is already available).

11.5 Data safety and monitoring

The investigator will provide oversight for the study evaluation of this health system initiative. Physician practices will follow their standards of care to manage patients initiated on statins.

11.6 Risk/benefit

11.6.1 Potential study risks

The potential risks associated with this study are minimal. Breach of data is a potential risk that will be mitigated by using HIPAA compliant and secure data platforms for the intervention (Penn Medicine servers) and evaluation (LDI HSRDC server). Statins do have known potential side effects, mostly commonly myopathy. To reduce this risk, patients with document allergies or adverse events will be excluded from the initiative and study. Patients with renal failure will also be excluded as they may require lower doses of statins than patients without renal failure. Prescribing statins and monitoring for known side effects are otherwise standard of care within primary care practices.

11.6.2 Potential study benefits

Statins have been demonstrated as an effective tool for reducing cardiovascular events. Early intervention with statins can potentially be life saving for patients who are at risk or already have a diagnosis of cardiovascular disease. An intervention that prompts physicians to actively think about evidence-based guidelines and high-value treatment could contribute positively to patient care and outcomes. However, it is possible that patients will receive no benefit from this study.

11.6.3 Risk/benefit assessment

The risk/benefit ratio is highly favorable given the potential benefit from eligible patients being prescribed a statin, that prescription and monitoring of a statin is within the standards of care in a

primary care practice, and that efforts have been put into place to minimize the risk of breach of data.
